## 9.7 Safety Oversight

### 9.7.1 Independent Safety Monitor (ISM)

An independent Safety Monitor will be appointed for oversight of subject safety in this trial. The ISM will be a local, qualified physician who will be available to advise the investigators on trial-related medical questions or problems. The ISM will work with the DMID Medical Monitor to

ensure adequacy of adverse event monitoring and reporting. Should the ISM not be available, he/she will recommend an alternative to serve as a substitute ISM.

The ISM's primary responsibility will be to monitor subject safety. The Principal Investigator is responsible for ensuring that the ISM is aware of any new safety information that becomes available during the course of the trial.

### **9.7.2 Safety Monitoring Committee (SMC)**

At least three individuals will be selected to serve as the study Safety Monitoring Committee (SMC) to advise the Sponsor and the study investigators on the trial. All SMC members will be independent from the Sponsor and study site. The SMC's primary responsibility will be to monitor subject safety. The Principal Investigator is responsible for ensuring that the SMC is aware of all new safety information. The SMC will periodically review data on safety and enrollment, and will review cumulative safety data for evidence of study related AEs, adherence to the protocol, and factors that may affect outcome or study data such as protocol violations and losses to follow up.

The SMC will review safety data at the following time points:

- Ad hoc when a study halting rule is met (see Section 9.5) or for immediate concerns regarding observations during this trial, or as needed.
- 1-2 weeks before the first CHHI application to review safety data collected to date.
- After the first 20 subjects have completed their study Day 175 (5 weeks after CHHI) visits.
- Final review meeting: 6 to 8 months after clinical database lock to review the cumulative unblinded safety data for the study.

Data will be provided in a standard summary format. The SMC may be asked to provide recommendations in response to questions posed by the study Principal Investigator, the Sponsor, or DMID.

The SMC will operate under the rules of a DMID-approved charter that will be written at the organizational meeting of the SMC. At this time, each data element that the SMC needs to assess will be clearly defined. Procedures for SMC reviews and meetings will be defined in the charter. The SMC will review applicable data to include, but not limited to, study progress and subject, clinical, safety, and reactogenicity data. Reports may include enrollment and demographic information, medical history, concomitant medications, physical assessments, clinical laboratory values, subject compliance with study procedures/interventions, and solicited and unsolicited AE/SAEs. Additional data may be requested by the SMC, and interim statistical reports may be generated as deemed necessary and appropriate by the Sponsor. The SMC will receive data in aggregate and presented by group. The SMC may also be provided with expected and observed rates of the expected AEs in an unblinded fashion, and may request vaccine assignment be unblinded for an individual subject if required for safety assessment. The SMC will review grouped and unblinded data in the closed session only. As an outcome of

each review/meeting, the SMC will make a recommendation as to the advisability of proceeding with study vaccinations or CHHI (as applicable), and to continue, modify, or terminate this trial.

The study Sponsor, Principal Investigator or the SMC chair may convene the SMC on an ad hoc basis according to protocol criteria or if there are immediate concerns regarding observations during the course of this trial. The ISM and DMID Medical Monitor will be responsible for reviewing SAEs in real time. The SMC will review SAEs on a regular basis and ad hoc during this trial.

It is the Principal Investigator's (or designated agent) responsibility to ensure that the SMC reviews the current safety data (grouped by dose cohort), study protocol, and any other requested documents at its meetings. Occurrence of an SAE will be reported to the SMC at the same time that it is reported to the IRB. Additionally, any new information that may adversely affect the safety of the subjects or the conduct of the study will be submitted to the SMC as it becomes available.

## 10 CLINICAL MONITORING

### 10.1 Site Monitoring Plan

The Sponsor (or its designee) will monitor all aspects of the study, with respect to current Good Clinical Practices, and for compliance with applicable government regulations. Prior to the start of the study, the Principal Investigator will be informed of the frequency of monitoring visits and will be given reasonable notification prior to each visit. The objectives of a monitoring visit will be to verify the prompt reporting of SAEs, to check the availability of the signed Informed Consent for enrolled study subjects, to compare CRFs and spreadsheets with source data for completeness and accuracy, to verify compliance with the clinical protocol, and to check investigational product accountability. During the monitoring visit, the Principal Investigator (and/or designee) and other study personnel should be available to discuss the study. Study documents must be available for review throughout the course of the study.

## 11 STATISTICAL CONSIDERATIONS

### 11.1 Study Hypotheses

This study is not designed to test statistically significant small differences in efficacy between different adjuvant formulations of the *Na*-GST-1 hookworm vaccine as assessed in the CHHI model. Rather, it is intended to provide an indication of an impact on infection as assessed by CHHI, and to detect large differences in efficacy with acceptable power. Furthermore, the study intends to assess the safety, reactogenicity, and immunogenicity of three novel adjuvant formulations of *Na*-GST-1: *Na*-GST-1 formulated on Alhydrogel, *Na*-GST-1/Alhydrogel® administered with AP 10-701, and *Na*-GST-1/Alhydrogel® administered with CpG 10104.

The chosen sample size principally facilitates the assessment of efficacy (as estimated by infection status determined by the saturated saline flotation technique for hookworm egg detection in fecal samples following CHHI) as well as safety, as discussed in Section 11.2, *Sample Size Considerations*. Given that, this study will attempt to assess the following hypotheses:

1. Administration of the *Na*-GST-1/Alhydrogel® vaccine with either AP 10-701 or CpG 10104 will result in a reduced proportion of volunteers infected with hookworm following CHHI, as determined by the saline flotation technique, compared to placebo controls.
2. Co-administration of *Na*-GST-1/Alhydrogel® vaccine with either AP 10-701 or CpG 10104 will increase the IgG antibody response to *Na*-GST-1 compared to when *Na*-GST-1/Alhydrogel® is administered alone.
3. Co-administration of *Na*-GST-1/Alhydrogel® vaccine with either AP 10-701 or CpG 10104 will increase the affinity of induced IgG antibodies to *Na*-GST-1 compared to when *Na*-GST-1/Alhydrogel® is administered alone.
4. Co-administration of the *Na*-GST-1/Alhydrogel® vaccine with either AP 10-701 or CpG 10104 will increase the induction of specific MBCs to *Na*-GST-1 compared to when *Na*-GST-1/Alhydrogel® is administered alone.
5. Co-administration of the *Na*-GST-1/Alhydrogel® vaccine with either AP 10-701 or CpG 10104 increases the neutralizing capacity of induced IgG antibodies to *Na*-GST-1 compared to when *Na*-GST-1/Alhydrogel® is administered alone.
6. Co-administration of *Na*-GST-1/Alhydrogel® vaccine with either AP 10-701 or CpG 10104 will increase the avidity of induced IgG antibodies to *Na*-GST-1 compared to when *Na*-GST-1/Alhydrogel® is administered alone.

### 11.2 Sample Size Considerations

Sample size considerations are based on the proportion of subjects with detectable hookworm eggs at any time, as measured by the saturated saline flotation technique. The primary analysis of the proportions will consist of comparing the proportion in each of the three *Na*-GST-1

intervention groups to the proportion in the placebo control group (group 4) using a one-sided Fisher exact test, for a total of three comparisons. The Holm-Bonferroni procedure will be used to control the familywise error rate at 0.05. Based on the results from the initial CHHI trial that was conducted at GWU (NCT01940757), we expect an infected proportion of 90% in group 4 (i.e., infectivity controls), and a proportion less than 20% in at least one of the intervention groups. At alpha=0.05/3, this yields a power of 87.7%. The power is 73.2% for an infection rate of 30% in intervention and 96.3% for an infection rate of 10%.

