### 11.4 Final Analysis Plan

The purpose of this trial is to estimate vaccine efficacy as assessed by CHHI, adverse event rates and patterns of immune responses as well as to compare these rates and patterns between the investigational Na-GST-1 vaccine formulations.

This section briefly describes the statistical methods to be used; a detailed analytical plan will fully describe the methods. The analytical plan will discuss the planned approaches to missing data. Deviations from the original analytical plan will be thoroughly documented and reported to the Sponsor.

Descriptive and hypothesis-testing approaches will be used to meet the protocol objectives as stated in **Section 3**. Estimates will be presented with their 95% confidence intervals. Formal statistical tests, as outlined below, will be used to compare the different Na-GST-1 vaccine formulations, as compared to saline placebo. Statistical tests will use a significance level of 5% (either two-sided or one-sided, depending on the analysis being conducted; this will be specified *a priori*).

**Primary Objective #1:** To compare the impact of vaccination with Na-GST-1/Alhydrogel® delivered with or without AP 10-701 or CpG 10104 on controlled human hookworm infection (CHHI) with *N. americanus* larvae in healthy, hookworm-naïve adults, as determined by the presence of eggs using a qualified flotation technique.

*Primary Outcome #1 Measure:*

The following parameters will be evaluated for each formulation of Na-GST-1:

1. Proportion of subjects with detectable hookworm eggs, at any time point, in fecal samples, as determined by microscopy using the qualified saline float technique.

*Analysis Plan:*

- a. The proportion of participants with detectable hookworm eggs in fecal samples by microscopy, at any time point post-CHHI, will be summarized as a descriptive measure by study group.

IRB NUMBER: 121643

IRB APPROVAL DATE: 11/17/2025

- b. The proportion of participants with detectable hookworm eggs in fecal samples by microscopy will be summarized as a descriptive measure by study group at each time point.

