- c. The proportion of subjects with detectable hookworm eggs in each of the intervention groups (Groups 1, 2 and 3) will be compared to the proportion of subjects in the placebo control group (Group 4) using a one sided Fisher exact test. The p-values from the three tests will be adjusted using the Holm-Bonferroni procedure to control the familywise error rate at 0.05. Power calculations are based on this outcome.

Primary Objective #2: To evaluate the safety and reactogenicity of Na-GST-1/ Alhydrogel® delivered with or without AP 10-701 or CpG 10104 on Days 0, 56 and 112, in healthy, hookworm-naïve adults.

AEs will be coded according to Medical Dictionary of Regulatory Activities (MedDRA™) preferred terms. The frequency, severity, and relationship of AEs per each vaccine formulation of Na-GST-1 will be presented in tabular form using the MedDRA™ coded term and organized by MedDRA™ System, Organ, and Class (SOC) designations.

1. The frequency of solicited local injection site and systemic AEs, and unsolicited AEs will be summarized by SOC and preferred term.
2. Line listings of clinical and laboratory AEs classified as solicited injection site, solicited systemic, or unsolicited and will be displayed in tables stratified by formulation group (i.e., Na-GST-1/Alhydrogel, Na-GST-1/Alhydrogel plus AP 10-701, Na-GST-1/Alhydrogel plus CpG 10104, or saline placebo).
3. AEs will be summarized by severity and relationship to vaccine by individuals and formulation of Na-GST-1.
4. The frequency of vaccine-related SAEs and AESIs will be tallied as well as summarized by body system, by vaccine formulation.

*Primary Outcome #2 Measures:*

The following summary parameters will be evaluated for each formulation of Na-GST-1, in comparison to saline placebo control:

1. Frequency of solicited injection site and systemic reactogenicity, graded by severity, on the day of each study vaccination through 14 days after each study vaccination.
2. Frequency of solicited adverse events, graded by severity, on the day of CHHI through study Day 280.
3. Frequency of study vaccine-related Serious Adverse Events from the time of the first study vaccination through approximately 10 months after the last study vaccination.
4. Frequency of clinical safety laboratory adverse events.

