### **5.7.4 Primary and Secondary Analysis**

#### **5.7.4.1 Primary Endpoint Analysis**

The primary efficacy endpoint analysis of proportion of subjects with detectable hookworm eggs in fecal samples, at any time point post-CHHI, will be summarized using frequency counts and percentages as a descriptive measure at time points post-CHHI for all vaccination groups.

Along with the summaries for any time points post-CHHI, the proportion of subjects with detectable hookworm eggs in fecal samples will be summarized as a descriptive measure by study group at each time point.

The proportion of subjects with detectable hookworm eggs in each of the vaccination groups (Groups 1, 2 and 3) will be compared to the proportion of subjects in the placebo control group (Group 4) using a two-sided Fisher exact test. The p-values for the pairwise comparison of proportions of subjects in the vaccination groups (Group 1, 2 and 3) and placebo group (Group 4) will be reported. No adjustments for multiple comparisons will be made and therefore, the reported p-values will have to be interpreted with caution.

The proportion of subjects with at least one injection site AE and the frequency of the AE grouped by PT will be compared by *Na*-GST-1 vaccine formulation and placebo. The null hypotheses that the type and number of adverse events is the same across all groups will be tested using Fisher's exact test.

Laboratory results (haematological and clinical chemistry) will be descriptively examined and any clinically significant values for individuals will be reported.

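### With 12 per group, the protocol's Fisher test uses about a third of its allowed error; Boschloo's exact test would add roughly 6, 12 and 2 points of power at 20%, 30% and 10% infected, an improvement rather than a correction

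*Protocol*

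**What the plan says.** Protocol 11.2 sets the primary analysis as three comparisons with placebo, "using a one-sided Fisher exact test, for a total of three comparisons". On multiplicity it says: "The Holm-Bonferroni procedure will be used to control the familywise error rate at 0.05". The design case, where the final phrase refers to the vaccine arms, reads: "we expect an infected proportion of 90% in group 4 (i.e., infectivity controls), and a proportion less than 20% in at least one". For that case it states "At alpha=0.05/3, this yields a power of 87.7"%, followed by the other two scenarios: "The power is 73.2% for an infection rate of 30% in intervention and 96.3% for an infection rate of 10"%. Protocol 11.4 repeats the test for Primary Objective #1 ("using a one sided Fisher exact test", Holm-adjusted) and adds, for all estimates: "Estimates will be presented with their 95% confidence intervals".

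SAP 5.7.4.1 analyses the same endpoint "using a two-sided Fisher exact test", without any multiplicity adjustment. SAP 3.1 also gives a two-sided test, with an alpha of about 0.1. SAP 7, which lists changes from the protocol, mentions neither difference. For the primary efficacy endpoint SAP 5.7.4.1 specifies counts, percentages and p-values only.

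Neither document discusses how conservative Fisher's test is at this size, or any unconditional exact test.

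**The concern.** Block randomisation fixes the group sizes, while the number infected is random. Fisher's test conditions on the total number infected. With 12 per group only a few p-values are then possible for each total, and most of the allowed 1.67% cannot be used. An exact test that does not condition on the total can recover part of it without enrolling anyone.

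At stake is the chance of recognising a formulation that works. Protocol 2.2.5 makes evidence of efficacy for at least one formulation a condition for wider paediatric testing. The 90% placebo rate rests on 9 of 10 subjects (Protocol 2.1.9.1), so the real margin may be thinner than the design case suggests.

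Separately, Protocol 11.4 gives estimating vaccine efficacy as a purpose of the trial, and the SAP plans no such estimate or interval for the primary endpoint.

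**Working it through.** **Inputs.** 12 per group and one-sided alpha of 0.05/3 = 0.01667 at the first Holm step; placebo 90% infected; vaccine 20%, 30% and 10% (all Protocol 11.2 and the Protocol Summary).

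**Formulas.** Let x of 12 be infected on vaccine, y of 12 on placebo, and t = x + y.
- Fisher: p_F(x,y) = Σ_{k≤x} C(12,k)·C(12,t−k) / C(24,t). Reject if p_F ≤ 0.01667.
- Boschloo: p_B(x,y) = maximum over a common rate p of P_p[p_F(X,Y) ≤ p_F(x,y)]. Reject if p_B ≤ 0.01667.
- Power: sum of the two binomial probabilities over all rejected outcomes among the 13 × 13 = 169.
- Size: the same sum with equal rates, maximised over that rate.

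**The plan's own figures.** Exact Fisher power is 88.8%, 74.1% and 97.5% at 20%, 30% and 10%, against the stated 87.7%, 73.2% and 96.3%. The stated figures are 0.9 to 1.2 points low, so they reproduce.

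**Size.** Fisher's maximum is 0.51% (at a common rate near 0.36), and 0.51/1.67 is about 31% of the allowance. Boschloo's maximum is 1.44%. Familywise error for three tests at this step with a shared placebo group is Σ_y b(y)·[1 − (1 − r(y))³], where b(y) is the binomial probability of y infected on placebo and r(y) is the chance that one vaccine group rejects given y. Its maximum is 1.4% for Fisher and 3.9% for Boschloo, both under 5%.

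**Power, placebo 90%, 12 vs 12.**

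| Vaccine infected | Fisher | Boschloo | Gain (points) |
|---|---|---|---|
| 10% | 97.5% | 99.3% | 1.7 (before rounding) |
| 20% | 88.8% | 95.2% | 6.4 |
| 30% | 74.1% | 85.6% | 11.5 |

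Outside the protocol's scenarios, as assumptions: at 40% on vaccine, 54.8% vs 70.5%; with 80% on placebo and 20% on vaccine, 68.0% vs 81.8%.

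**What changes.** Seven outcomes become significant and none is lost. One is 4/12 infected on vaccine against 10/12 on placebo. There t = 14 and p_F = (66 + 2,640 + 32,670)/1,961,256 = 0.0180, which misses 0.0167, while p_B = 0.0084. Another is 3/12 against 9/12, with p_F = 0.0196 and p_B = 0.0114.

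**In subjects.** Fisher with 14 per group (56 in all) has 95.7% and 85.3% power at 20% and 30%, about what Boschloo gives with 48.

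**Sensitivity of the gain.** The evaluable numbers below 12 are assumptions. Protocol 5.3.1 does not replace leavers, and Protocol 5.3.3 allows the challenge to be withheld.

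| Setting | Fisher size | Gain at 20% | Gain at 30% |
|---|---|---|---|
| 11 vaccine vs 12 placebo | 0.57% | 4.7 | 10.5 |
| 11 vs 11 | 0.85% | 1.9 | 6.9 |
| 10 vs 10 | 0.64% | 3.7 | 7.9 |
| SAP test: two-sided 0.05, unadjusted, 12 vs 12 | 2.28% | 1.9 (94.6% to 96.5%) | 6.9 (82.6% to 89.5%) |

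At two-sided 0.10, the alpha in SAP 3.1, the gains are 0.5 points (98.1% to 98.6%) and 2.9 points (92.0% to 95.0%).

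**The case against.** **The planned test is valid and adequate for its target.** This stands. Fisher controls the error and has more than 80% power in the design case. Protocol 11.1 asks only for large differences to be detected with acceptable power. A reader might infer from the conservatism that the stated power is wrong or the trial underpowered; the reproduction shows neither.

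**The gain is not stable.** This stands in part. A reader might take 6 to 12 points as general. It fits the 20% and 30% scenarios with exactly 12 evaluable per group under the protocol's test. At 10% there is little left to gain, and small losses of subjects shrink it. It stayed positive in every setting checked.

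**Other routes gain more.** A reader might infer that this is the largest gain available without more subjects. That is unsupported: Fisher at one-sided 0.05 for the first hypothesis of a fixed sequence would give 98.1% and 92.0% at 20% and 30%. That route needs a prespecified order and favours one formulation, so it is a different design choice and does not count against Boschloo.

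**The error control is unconditional.** Boschloo rejects 1/12 vs 6/12 and 6/12 vs 11/12, where Fisher's p is 0.034. Given those totals, its conditional error exceeds 0.0167. The subjects are recruited volunteers rather than a random sample, so a conditional analysis is defensible. This is a real cost to disclose. It does not defeat a test that controls exact binomial error with fixed group sizes, particularly with the Fisher p-value reported alongside.

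**The SAP contains no Holm procedure.** This stands, and it sets the order of the repair.

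**Conclusion.** The point holds as a cheap improvement. With 12 evaluable per group and the protocol's one-sided 0.05/3 step, Boschloo's test keeps the error limit (1.44% per comparison, at most 3.9% familywise at that step). It adds about 6 points of power at 20% infected, 12 at 30% and 2 at 10%. With 10 or 11 evaluable per group the gain is about 2 to 4 points at 20% and 7 to 8 at 30%. Under the SAP's two-sided unadjusted test at 5% it is about 2 and 7. All these figures assume independent binomial counts and a 90% placebo rate.

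Which figures apply depends on the unresolved conflict between protocol and SAP over sidedness and multiplicity, so that conflict comes first. The missing efficacy estimate and interval in SAP 5.7.4.1 is a separate gap against Protocol 11.4 and stands whichever test is used.

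**What to change.** Before unblinding, in this order:

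1. Reconcile SAP 3.1 and 5.7.4.1 with Protocol 11.2 and 11.4 on sidedness, multiplicity and alpha, and record the outcome in SAP 7. The steps below assume that the protocol's one-sided test with Holm at 0.05 is kept.
2. In Protocol 11.2 and 11.4 and SAP 5.7.4.1, name the one-sided Boschloo exact test within Holm as primary. Report the Fisher p-value for each comparison as supportive. Update the power statement, including a case with fewer than 12 evaluable per group.
3. Whichever test is chosen, add to SAP 5.7.4.1 the vaccine efficacy (1 − risk ratio) and the risk difference against placebo for each formulation, with exact 95% confidence intervals.

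The cost is a few sentences in each document and a short validated routine, with no extra subjects. The downsides are a test that is less familiar to readers and error control that is unconditional rather than conditional on the total infected. If the blind has already been broken, keep Fisher as primary and show Boschloo only as a sensitivity analysis; step 3 still applies.

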### 11.3 Planned Interim Analyses

None planned.

### 11.4 Final Analysis Plan

The purpose of this trial is to estimate vaccine efficacy as assessed by CHHI, adverse event rates and patterns of immune responses as well as to compare these rates and patterns between the investigational Na-GST-1 vaccine formulations.

This section briefly describes the statistical methods to be used; a detailed analytical plan will fully describe the methods. The analytical plan will discuss the planned approaches to missing data. Deviations from the original analytical plan will be thoroughly documented and reported to the Sponsor.

Descriptive and hypothesis-testing approaches will be used to meet the protocol objectives as stated in **Section 3**. Estimates will be presented with their 95% confidence intervals. Formal statistical tests, as outlined below, will be used to compare the different Na-GST-1 vaccine formulations, as compared to saline placebo. Statistical tests will use a significance level of 5% (either two-sided or one-sided, depending on the analysis being conducted; this will be specified *a priori*).

**Primary Objective #1:** To compare the impact of vaccination with Na-GST-1/Alhydrogel® delivered with or without AP 10-701 or CpG 10104 on controlled human hookworm infection (CHHI) with *N. americanus* larvae in healthy, hookworm-naïve adults, as determined by the presence of eggs using a qualified flotation technique.

*Primary Outcome #1 Measure:*

The following parameters will be evaluated for each formulation of Na-GST-1:

1. Proportion of subjects with detectable hookworm eggs, at any time point, in fecal samples, as determined by microscopy using the qualified saline float technique.

*Analysis Plan:*

- a. The proportion of participants with detectable hookworm eggs in fecal samples by microscopy, at any time point post-CHHI, will be summarized as a descriptive measure by study group.

IRB NUMBER: 121643

IRB APPROVAL DATE: 11/17/2025

- b. The proportion of participants with detectable hookworm eggs in fecal samples by microscopy will be summarized as a descriptive measure by study group at each time point.
- c. The proportion of subjects with detectable hookworm eggs in each of the intervention groups (Groups 1, 2 and 3) will be compared to the proportion of subjects in the placebo control group (Group 4) using a one sided Fisher exact test. The p-values from the three tests will be adjusted using the Holm-Bonferroni procedure to control the familywise error rate at 0.05. Power calculations are based on this outcome.

Primary Objective #2: To evaluate the safety and reactogenicity of Na-GST-1/ Alhydrogel® delivered with or without AP 10-701 or CpG 10104 on Days 0, 56 and 112, in healthy, hookworm-naïve adults.

AEs will be coded according to Medical Dictionary of Regulatory Activities (MedDRA™) preferred terms. The frequency, severity, and relationship of AEs per each vaccine formulation of Na-GST-1 will be presented in tabular form using the MedDRA™ coded term and organized by MedDRA™ System, Organ, and Class (SOC) designations.

1. The frequency of solicited local injection site and systemic AEs, and unsolicited AEs will be summarized by SOC and preferred term.
2. Line listings of clinical and laboratory AEs classified as solicited injection site, solicited systemic, or unsolicited and will be displayed in tables stratified by formulation group (i.e., Na-GST-1/Alhydrogel, Na-GST-1/Alhydrogel plus AP 10-701, Na-GST-1/Alhydrogel plus CpG 10104, or saline placebo).
3. AEs will be summarized by severity and relationship to vaccine by individuals and formulation of Na-GST-1.
4. The frequency of vaccine-related SAEs and AESIs will be tallied as well as summarized by body system, by vaccine formulation.

*Primary Outcome #2 Measures:*

The following summary parameters will be evaluated for each formulation of Na-GST-1, in comparison to saline placebo control:

1. Frequency of solicited injection site and systemic reactogenicity, graded by severity, on the day of each study vaccination through 14 days after each study vaccination.
2. Frequency of solicited adverse events, graded by severity, on the day of CHHI through study Day 280.
3. Frequency of study vaccine-related Serious Adverse Events from the time of the first study vaccination through approximately 10 months after the last study vaccination.
4. Frequency of clinical safety laboratory adverse events.
5. Frequency of unsolicited adverse events, graded by severity, from the time of each study vaccination through approximately 1 month after each study vaccination; and from the time of CHHI through treatment with albendazole (Day 297).

6. Frequency of new-onset chronic medical conditions through approximately 10 months after the third study vaccination.
7. Frequency of Adverse Events of Special Interest through approximately 10 months after the third study vaccination.

*Analysis Plan:*

- a. The proportion of subjects with at least one injection site AE will be compared by Na-GST-1 vaccine formulation. We will test the null hypotheses that the type and number of adverse events is the same across all groups by Fisher's exact test.
- b. We will test the null hypothesis that the frequency of adverse events grouped by SOC term is the same in all groups using exact Poisson tests of the ratio of the rates. There will be no adjustment for multiple comparisons.
- c. Laboratory results (hematological and clinical chemistry) will be examined for trends over time and any clinically significant values for individuals will be reported.

Secondary Objective #1: To compare the impact of vaccination with Na-GST-1/Alhydrogel® delivered with or without AP 10-701 or CpG 10104 on fecal egg counts, as determined by the McMaster method, after CHHI with *N. americanus* larvae in healthy, hookworm-naïve adults.

*Secondary Outcome #1 Measure:*

The following parameters will be evaluated for each formulation of Na-GST-1, in comparison to the saline placebo control:

1. Fecal egg counts as determined by microscopy using the McMaster method, during Weeks 5 through 20 post-CHHI.

*Analysis Plan:*

- a. Fecal egg counts as determined by microscopy of the subjects in each of the intervention groups (Groups 1, 2 and 3) will be compared to the eggs counts of the subjects in Group 4 using a Wilcoxon-Mann-Whitney rank-sum test. The p-values from the three tests will be adjusted using the Holm-Bonferroni procedure to control the familywise error rate at 0.05.

Secondary Objective #2: To assess the relationship between antibody responses to Na-GST-1 induced by vaccination with Na-GST-1/Alhydrogel® delivered with or without AP 10-701 or CpG 10104 and responses to CHHI in healthy, hookworm-naïve adults, as determined by the presence of eggs using a qualified flotation technique.

Secondary Objective #3: To assess the duration of antibody responses to Na-GST-1 induced by vaccination with Na-GST-1/Alhydrogel® delivered with or without AP 10-701 or CpG 10104.

*Secondary Outcome #2 and #3 Measures:*

The following parameters will be evaluated for each formulation of Na-GST-1, in comparison to the saline placebo control:

1. The anti-Na-GST-1 IgG antibody response, by a qualified indirect enzyme-linked immunosorbent assay (ELISA) at approximately 14 days after each vaccination, and approximately 1, 2, 4, 6, 7, 8 and 10 months after the third dose.

*Analysis Plan:*

- a. The proportion of participants with detectable anti-Na-GST-1 IgG responses will be summarized as a descriptive measure.
- b. IgG levels will be displayed graphically by study group using notched box plots at each time point.
- c. Geometric mean antibody responses will be compared between vaccine formulation groups at each time point. Comparisons between groups will be made by a one-way analysis of variance (ANOVA) with pair-wise comparisons between groups made by contrasts.
- d. Geometric mean antibody responses for each antigen will be compared using a regression model with main effects for the doses of Na-GST-1 (0 or 100µg), AP 10-701 (0 or 5 µg), and CpG 10104 (0 or 500µg).
- e. For antigen-specific log IgG levels, a three-way ANOVA will be conducted, with Na-GST-1, CpG 10104 and AP 10-701 doses as factors.
- f. Pair-wise comparisons of IgG levels on study Day 126 (2 weeks after the third vaccination) across all combinations of Na-GST-1 doses (i.e., 0 [placebo] or 100 µg), AP 10-701 doses (i.e., 0 or 5 µg), and CpG 10104 doses (0 or 500µg) will be assessed using Tukey's HSD.
- g. Percent change in IgG antibody levels from days of vaccination to days 7, 14 and 28 post-vaccination will be compared between vaccine formulation and dose groups. Values will be reported with 95% confidence intervals.
- h. Percent change in IgG antibody levels from vaccination day #1 to #2, from vaccination day #2 to #3, and from vaccination day #3 to day of CHHI will be compared between vaccine formulation and dose groups to assess the sustainability of the response from trough to trough and post-CHHI. Values will be reported with 95% confidence intervals.
- i. Percent change in IgG antibody levels from the peak following the third vaccination, to 1, 2, 4, 6, 7, 8 and 10 after the third vaccination. Values will be reported with 95% confidence intervals.
- j. Percent change in IgG antibody levels from the day of CHHI to 1, 3, 5, 6, 7 and 9 months post-CHHI. Values will be reported with 95% confidence intervals.
- k. A longitudinal model will be built to describe the IgG levels over time. Using a longitudinal panel model, differences in antibody isotype levels by formulation of Na-GST-1 will be explored. This will be accomplished using Proc Mixed in SAS 9.3 so the analysis will take account of the correlation between measurements on the same subject.
- l. Logistic regression will be explored for the binary response of hookworm infection post-CHHI as a function of antibody response, and a Poisson regression of the event counts (i.e., infection) as a function of IgG antibody response. In these models, vaccination group will be a covariate, rather than just using the IgG responses.

**Exploratory Objective #1:** To assess the relationship between the functional capacity of vaccine-induced antibodies that neutralize the *in vitro* activity of native Na-GST-1 enzyme and responses to CHHI in healthy, hookworm-naïve adults.

*Exploratory Outcome #1 Measure:*

The following parameters will be evaluated for each formulation of Na-GST-1, in comparison to the saline placebo control:

1. The functional capacity of vaccine-induced antibodies to neutralize the *in vitro* activity of the native Na-GST-1 enzyme.

*Analysis Plan:*

- a. Percent inhibition of native enzyme activity will be displayed graphically for the various study groups at each time point.
- b. Three-way ANOVAs with Na-GST-1, CpG 10104, and AP 10-701 as factors and percent inhibition as the outcome will be estimated.
- c. A longitudinal model will be built to describe percent inhibition of native enzyme activity over time. Using a longitudinal panel model, differences in percent inhibition by formulation of Na-GST-1 will be explored. This will be accomplished using Proc Mixed in SAS 9.3, so the analysis will take account of the correlation between measurements on the same subject.

**Exploratory Objective #2:** To compare the impact of vaccination with Na-GST-1/Alhydrogel® delivered with or without AP 10-701 or CpG 10104 on levels of hookworm DNA as detected by real-time PCR in healthy, hookworm-naïve adults challenged with CHHI.

*Exploratory Outcome #2 Measure:*

The following parameters will be evaluated for each formulation of Na-GST-1, in comparison to the saline placebo control:

1. Levels of *N. americanus* DNA in fecal samples, as measured by real-time PCR, during Weeks 5 through 20 post-CHHI.

*Analysis Plan:*

- a. The proportion of participants with detectable hookworm DNA in fecal samples by PCR, at any time point post-CHHI, will be summarized as a descriptive measure by study group.
- b. The proportion of participants with detectable hookworm DNA in fecal samples by PCR will be summarized as a descriptive measure by study group at each time point.
- c. Estimated fecal egg counts as determined by PCR of the subjects in each of the vaccination groups (Groups 1, 2 and 3) will be compared to the eggs counts of the subjects in Group 4 using a Wilcoxon-Mann-Whitney rank-sum test. Current PCR hookworm spiking studies and previous egg/DNA correlations are used to determine estimated egg counts (74). The p-values from the three tests will be adjusted using the Holm-Bonferroni procedure to control the familywise error rate at 0.05.

**Exploratory Objective #3** To assess the impact of vaccination with Na-GST-1/Alhydrogel® delivered with or without AP 10-701 or CpG 10104 on the affinity of antibody-antigen interactions, and how affinity relates to responses to CHHI in healthy, hookworm-naïve adults, as determined by the presence of eggs using a qualified flotation technique.

